8.5.2 Method of Detecting AEs, SAEs, and Other Reportable Safety Events

Care will be taken not to introduce bias when detecting AEs and/or SAEs and other reportable safety events. Open-ended and nonleading verbal questioning of the participant is the preferred method to inquire about AE occurrence.

8.5.3 Follow-up of AE, SAE, and Other Reportable Safety Event Information

After the initial AE/SAE report, the investigator is required to proactively follow each participant at subsequent visits/contacts. All AEs, SAEs, and other reportable safety events, including pregnancy and exposure during breastfeeding, ECIs, cancer, and overdose will be followed until resolution, stabilization, until the event is otherwise explained, or the participant is lost to follow-up (as defined in Section 7.3). In addition, the investigator will make every attempt to follow all nonserious AEs that occur in allocated participants for outcome. Further information on follow-up procedures is given in Appendix 3.

8.5.4 Regulatory Reporting Requirements for SAE

Prompt notification (within 24 hours) by the investigator to the Sponsor of SAE is essential so that legal obligations and ethical responsibilities towards the safety of participants and the safety of a study intervention under clinical investigation are met.

The Sponsor has a legal responsibility to notify both the local regulatory authority and other regulatory agencies about the safety of a study intervention under clinical investigation. The Sponsor will comply with country-specific regulatory requirements and global laws and regulations relating to safety reporting to regulatory authorities, IRB/IECs, and investigators.

Investigator safety reports must be prepared for SUSARs according to local regulatory requirements and Sponsor policy and forwarded to investigators as necessary.

An investigator who receives an investigator safety report describing an SAE or other specific safety information (eg, summary or listing of SAE) from the Sponsor will file it along with the IB and will notify the IRB/IEC, if appropriate according to local requirements.

8.5.5 Pregnancy and Exposure During Breastfeeding

Although pregnancy and infant exposure during breastfeeding are not considered AEs, any pregnancy or infant exposure during breastfeeding in a participant (spontaneously reported to the investigator or their designee) that occurs during the study are reportable to the Sponsor.

All reported pregnancies must be followed to the completion/termination of the pregnancy.

Any pregnancy complication will be reported as an AE or SAE.

The medical reason (example: maternal health or fetal disease) for an elective termination of a pregnancy will be reported as an AE or SAE. Prenatal testing showing fetus will be born with severe abnormalities/congenital anomalies that leads to an elective termination of a pregnancy will be reported as an SAE for the fetus.

Pregnancy outcomes of ectopic pregnancy, spontaneous abortion, missed abortion, benign hydatidiform mole, blighted ovum, fetal death, intrauterine death, miscarriage, and stillbirth must be reported as serious events (Important Medical Events). If the pregnancy continues to term, the outcome (health of infant) must also be reported.

8.5.6 Disease-related Events and/or Disease-related Outcomes Not Qualifying as AEs or SAEs

Not applicable.

8.5.7 Events of Clinical Interest

Selected serious and nonserious AEs are also known as ECIs and must be reported to the Sponsor.

Events of clinical interest for this study include:

1. An overdose of Sponsor's product, as defined in Section 8.6.
2. An elevated AST or ALT laboratory value that is greater than or equal to 3X the ULN and an elevated total bilirubin laboratory value that is greater than or equal to 2X the ULN and, at the same time, an alkaline phosphatase laboratory value that is less than 2X the ULN, as determined by way of protocol-specified laboratory testing or unscheduled laboratory testing.*

*Note: These criteria are based on available regulatory guidance documents. The purpose of the criteria is to specify a threshold of abnormal hepatic tests that may require an additional evaluation for an underlying etiology. The study-site guidance for assessment and follow up of these criteria can be found in the Investigator Study File Binder (or equivalent).

It may also be appropriate to conduct additional evaluation for an underlying etiology in the setting of abnormalities of liver blood tests including AST, ALT, bilirubin, and alkaline phosphatase that do not meet the criteria noted above. In these cases, the decision to proceed with additional evaluation will be made through consultation between the study investigators and the Sponsor Clinical Director. However, abnormalities of liver blood tests that do not meet the criteria noted above are not ECIs for this study.

8.6 Treatment of Overdose

For purposes of this study, an overdose will be defined as any dose of any drug administered as part of the study exceeding the dose prescribed by the protocol. It is up to the investigator or the reporting physician to decide whether a dose is to be considered an overdose, in consultation with the Sponsor.

Sponsor does not recommend specific treatment for an overdose. Decisions regarding dose interruptions or modifications will be made by the investigator in consultation with the Sponsor Clinical Director based on the clinical evaluation of the participant.

8.7 Pharmacokinetics

The decision as to which plasma and/or urine samples collected will be measured for evaluation of PK/pharmacodynamics will be collaboratively determined by the Sponsor (eg, samples at lower doses may not be measured if samples at higher doses reveal undetectable drug concentrations). If indicated, these samples may also be measured and/or pooled for assay in an exploratory manner for metabolites and/or additional pharmacodynamic markers.

8.7.1 Blood Collection for Plasma MK-2060 and Clopidogrel

Sample collection, storage, and shipment instructions for plasma samples will be provided in the Study Operations Manual by the Sponsor. Samples taken on the day of infusion will be collected in the opposite arm from the infusion site. The 1-hour PK sample will be obtained immediately prior to the end of infusion (i.e. no more than 15 min before anticipated time of the end of infusion). As plasma concentrations of the parent compound of clopidogrel are very low and are generally below the quantification limit beyond 2 hours after dosing, concentrations of the main circulating metabolite clopidogrel carboxylic acid will be assessed to monitor clopidogrel therapy.

8.8 Pharmacodynamics

Sample collection, storage, and shipment instructions for PT/aPTT/ FXI activity by central lab samples will be in the operations manual.

8.9 Biomarkers

Collection of samples for other biomarker research is also part of this study. The following samples for biomarker research are required and will be collected from all participants as specified in the SoA.

8.9.1 Planned Genetic Analysis Sample Collection

The planned genetic analysis sample will be drawn for CYP2C19 genotyping and for planned analysis of the association between genetic variants in DNA and drug response. If the IRB/IEC does not approve of the planned analysis of the association between DNA variation and drug response, or if there is a local law or regulation prohibiting the same, data analysis will be limited to CYP2C19. Leftover extracted DNA will be stored for FBR if the participant provides documented informed consent for FBR.

Sample collection, storage, and shipment instructions for planned genetic analysis samples will be in the Operations/Laboratory Manual.

8.9.2 Blood Collection for PT, aPTT, FXI Activity

PT and aPTT at screening, predose, and postdose specified in the SoA will be performed locally for safety monitoring. All other predose and postdose PT and aPTT, as well as FXI activity will be performed at a central vendor for PK/PD analysis. Sample collection, storage, and shipment instructions for the PT, aPTT, FXI activity will be provided in a separate Study

Operations Manual by the Sponsor. The primary data for statistical analysis and modeling will be based on the information from the central vendor.

8.9.3 Blood for Plasma ADA

Sample collection, storage, and shipment instruction for plasma samples will be provided in a separate Study Operations Manual by the Sponsor.

8.10 Future Biomedical Research Sample Collection

If the participant provides documented informed consent for FBR, the following specimens will be obtained as part of FBR:

- Leftover DNA for future research.
- Leftover main study plasma for future research.

8.11 Visit Requirements

Visit requirements are outlined in Section 1.3. Specific procedure-related details are provided in Section 8.

8.11.1 Screening and Run-in Period

Screening Visit:

Within 6 weeks before intervention allocation, potential participants will be evaluated to determine that they fulfill the entry requirements as set forth in Section 5.

Participants may be rescreened after consultation with the Sponsor. Rescreening should include all screening procedures listed in the SoA, including consent review.

Run-in Period:

Approximately 14 days before intervention allocation, potential participants who meet inclusion/exclusion criteria at the Screening Visit will report to the clinical research unit to perform on site hemodialysis on the days per SoA. Baseline Time to hemostasis will be measured during the run-in period. Refer to the SoA for other procedures required for the run-in period.

8.11.2 Treatment Period

Refer to the Schedule of Activities (Section 1.3) and Administrative and General Procedures (Section 8.1).

After all predose procedures have been completed, participants will be assigned a unique allocation number in a computer-generated allocation schedule.

Participants will be administered study drug as indicated in Section 6. Participants who on Day 1 have a significant acute illness or fever prior to the administration of study drug may be rescheduled.

8.11.3 Poststudy

The poststudy visit will occur approximately 96 days following administration of the last dose of study drug. Procedures outlined in the poststudy visit may be obtained on Day 104 (± 7 days). However, follow up on any clinical or laboratory AEs should occur in person if the poststudy visit occurs prior to 96 days following administration of the last dose of study drug.

8.11.4 Participants Discontinued From Study Intervention but Continuing to be Monitored in the Study

At any point if a participant discontinues from treatment but continues to be monitored in the study, all of study procedures specified in the SoA may be completed upon joint agreement between the investigator and the Sponsor. The subset of study procedures completed will be communicated in a PCL.

8.11.5 Critical Procedures Based on Study Objectives: Timing of Procedure

For this study, the blood sample for MK-2060 is the critical procedure.

At any postdose time point, the blood sample for MK-2060 needs to be collected as close to the exact time point as possible. All other procedures should be completed as close to the prescribed/scheduled time as possible. Study procedures can be performed before or after the prescribed/scheduled time.

The order of priority can be changed during the study with joint agreement of the investigator and the Sponsor Clinical Director.

Any nonscheduled procedures required for urgent evaluation of safety concerns take precedence over all routine scheduled procedures.

The following variance in procedure collection times will be permitted.

- Postdose PK and PD sample collection, standard safety evaluations (VS, ECG, laboratory safety tests (including chemistry/hematology, aPTT, PT), physical exam (full, symptom driven, systemic injection/infusion, local injection/infusion)) as outlined in [Table 6](#) and [Table 7](#) below.

Table 6 Pharmacokinetic (Blood), Pharmacodynamic and Biomarker Collection Windows

PK, PD and ADA Collection	PK, PD and ADA Collection Window
Days 1, 3, 5, 8: predose	Within 2 hr of dosing (samples to be collected before dialysis)
Day 1, 3, 5, 8: 1 hr post each dose	± 15 min (within 15 min of end of infusion)
Days 1, 3, 5, 8: 12 hr post dose	± 30 min
Days 2, 9, 10	± 4 hr of theoretical sampling time
Days 12, 15, 21, 29, 35	± 1 day
Days 49, 67	± 3 days
Day 104	± 7 days

- Predose standard safety evaluations: VS and ECG within 3 hours of MK-2060 dosing; laboratory safety tests (including aPTT and PT at local lab), drug screen and physical exam within 24 hours of MK-2060 dosing.

Table 7 Postdose Safety Evaluation Windows

Postdose Standard Safety Evaluations (VS, ECG, laboratory safety tests, and physical exam)	Postdose Evaluation Window
Days 1, 3, 5, and 8: all postdose	± 30 min of theoretical sampling time
Days 2, 9, and 10	± 4 hr of theoretical sampling time
Days 12, 15, 21, 29, 35	± 1 day
Days 49, 67	± 3 days
Day 104	± 7 days

- Assessment of time to adequate hemostasis: at the conclusion of the onsite hemodialysis session, after hemodialysis catheters are removed from the dialysis access site.
- Hemoccult test: samples may be obtained within 48 hours of specified timepoint or first available sample if not within the specified time window.
- Postdose evaluations: weight (Day 104), serum or urine pregnancy test (Day 104): use windows indicated in [Table 7](#).
- Study intervention administration: +/- 1 hour relative to time of dosing on Day 1.
- Run-in (Day -14 to Day -3 Visits): ± 1 day is allowed.

8.11.6 Study Design/Dosing/Procedures Modifications Permitted Within Protocol Parameters

This is a Phase 1 assessment of MK-2060 in participants with ESRD on HD, and the PK, pharmacodynamic, and safety profiles of the compound are still being elucidated. This protocol is written with some flexibility to accommodate the inherent dynamic nature of Phase 1 clinical studies. Modifications to the dose, dosing regimen, and/or clinical or laboratory procedures currently outlined may be required to achieve the scientific goals of the study and/or to ensure appropriate safety monitoring of the study participants.

As such, some alterations from the currently outlined dose and/or dosing regimen may be permitted based on newly available data, but the maximum daily dose may not exceed those currently outlined in the protocol.

- Decrease in the duration of study intervention administration (eg, number of days)
- Adjustment of the dosing interval (eg, divided doses [bid to qd, qd to bid, tid, or vice versa])
- Lengthening of the washout period between doses
- Addition of PK pause
- Instructions to take study intervention with or without food or drink may also be modified based on newly available data
- Modification of the PK/pharmacodynamic sample processing and shipping details based on newly available data

The PK/pharmacodynamic sampling scheme currently outlined in the protocol may be modified during the study based on newly available PK or pharmacodynamic data (eg, to obtain data closer to the time of peak plasma concentrations). If indicated, these collected samples may also be assayed in an exploratory manner for metabolites and/or additional pharmacodynamic markers.

Up to additional 50 mL of blood may be drawn for safety, PK, and/or pharmacodynamic analyses. The total blood volume withdrawn from any single participant will not exceed the maximum allowable volume during his/her participation in the entire study (Appendix 8).

The timing of procedures for assessment of safety procedures (eg, vital signs, ECG, safety laboratory tests, etc) may be modified during the study based on newly available data. Additional laboratory safety tests may be added to blood samples previously drawn to obtain additional safety information. These changes will not increase the number of study procedures for a given participant during his/her participation in the entire study.

It is understood that the current study may use some or none of the alterations described above. Any alteration made to this protocol to meet the study objectives must be detailed by

the Sponsor in a letter to the Study File and forwarded to the investigator for retention. The letter may be forwarded to the IRB/IEC at the discretion of the investigator.

9 STATISTICAL ANALYSIS PLAN

9.1 Statistical Analysis Plan Summary

This section contains a summary of the statistical analyses for this trial. Full details can be found in the subsequent sections. Since this is an exploratory study, statistical analyses will consist of presenting the descriptive statistics in shape of appropriate plots and summary tables (mean, standard deviation, median, min, max).

9.2 Responsibility for Analyses

The statistical analysis of the data obtained from this study will be conducted by, or under the direct auspices of, the Early Clinical Development Statistics Department in collaboration with the Quantitative Pharmacology and Pharmacometrics Department and Translational Pharmacology Department of the Sponsor.

If, after the study has begun, changes are made to the statistical analysis plan stated below, then these deviations to the plan will be listed, along with an explanation as to why they occurred, in the Clinical Study Report.

9.3 Hypotheses/Estimation

Objectives of the study are stated in Section 3.

Primary Objective: To assess the safety and tolerability following multiple doses of concomitant treatment of MK-2060 and clopidogrel by measuring the bleeding related AEs

Secondary Objective 1: To evaluate plasma pharmacokinetics of MK-2060 and clopidogrel following multiple doses of concomitant treatment of MK-2060 and clopidogrel

Estimation:

- Estimate plasma AUC₀₋₁₆₈, C_{max}, C₁₆₈, T_{max}, terminal t_{1/2}, CL, V_z.

Secondary Objective 2: To determine whether the increase in time required to achieve hemostasis in ESRD patients treated with MK-2060 and following completion of dialysis remains below 20 minutes

Hypothesis:

- Mean time-to-hemostasis for MK-2060 treatment is less than 20 minutes.

Tertiary/Exploratory Objective 1: To explore the effect of concomitant treatment of MK-2060 and clopidogrel on aPTT.

Estimation:

- Estimate aPTT fold change from baseline.

Tertiary/Exploratory Objective 2: To explore the effect of concomitant treatment of MK-2060 and clopidogrel on prothrombin time.

Estimation:

- Estimate PT fold change from baseline.

9.4 Analysis Endpoints

Primary Endpoints

1. Safety and tolerability following multiple doses of concomitant treatment of MK-2060 and clopidogrel are the primary endpoints. Thus all AEs including bleeding related AEs (as defined in Section 4.2.1.1) are the primary endpoints for this study.

Secondary Endpoints (Pharmacokinetic)

1. Pharmacokinetics: The pharmacokinetic variables of secondary interest for MK-2060 are plasma AUC₀₋₁₆₈, C_{max}, C₁₆₈, T_{max}, terminal t_{1/2}, CL, and V_z.
2. Time to hemostasis

Exploratory Endpoints:

1. Pharmacodynamics: The PD variable of exploratory interest is aPTT (change from baseline). Baseline is defined as the pre-dose value.
2. ADA

9.5 Analysis Populations

The following populations are defined for the analysis and reporting of data. All subjects will be reported, and their data analyzed, according to the treatment(s) they actually received.

All Subjects as Treated: The All Subjects as Treated Population consists of all subjects who received at least one dose of treatment. This population will be used for assessments of safety and tolerability.

Per-Protocol: The Per-Protocol Population consists of the set of data generated by the subset of subjects who comply with the protocol sufficiently to ensure that these data will be likely to exhibit the effects of treatment, according to the underlying scientific model. Compliance

covers such considerations as exposure to treatment, availability of measurements and absence of important protocol deviations. Important protocol deviations will be identified to the extent possible prior to unblinding by individuals responsible for data collection/compliance, and its analysis and interpretation. Any subjects or data values excluded from analysis will be identified, along with their reason for exclusion, in the CSR. At the end of the study, all subjects who are compliant with the study procedure as aforementioned and have available data from at least one treatment will be included in the Per-Protocol dataset.

9.6 Statistical Methods

Safety

Summary statistics and plots will be generated for raw laboratory safety tests, ECGs, and/or VS as well as for change from baseline, as deemed clinically appropriate. For the primary endpoint, i.e., the bleeding related AEs, descriptive summary (total counts, percentage) will be provided. Same will be provided for all AEs as well as for the secondary and exploratory endpoints wherever appropriate. For continuous measurements, mean, standard deviation, median, min, max will be provided. Depending on the safety parameter, the difference from baseline will either be computed on the original scale (raw change from baseline) or on the log scale and back-transformed for reporting (percent change from baseline) as appropriate. Values will be listed for each PK parameter (including Tmax and apparent terminal t_{1/2}), and appropriate non-model based descriptive statistics will be provided.

Secondary Hypothesis:

To determine whether the mean time-to-hemostasis recorded from patients treated with MK-2060 is lower than the cut-off time of 20 minutes, a Bayesian approach will be used. Utilizing a non-informative flat prior, the posterior probability that the observed mean of time-to-hemostasis of participants is less than 20 will be calculated, and the criteria for success will be met if the following condition is satisfied.

Posterior-probability (PP) ($\mu_{TH} < 20$) ≥ 0.60

Where

μ_{TH} = mean of the time-to-hemostasis measurements for ESRD patients treated with MK-2060

MK-2060 PK parameters including plasma AUC₀₋₁₆₈, C_{max}, C₁₆₈, Tmax, terminal t_{1/2}, CL, V_z with the following (non-model-based) descriptive statistics will be provided: N (number of subjects with non-missing data), geometric mean, and geometric percent CV (calculated as 100 x sqrt(exp(s₂) - 1), where s₂ is the observed variance on the natural log-scale).

Exploratory Estimation:

Descriptive statistics as well as appropriate plots will be displayed for aPTT fold change from baseline. To describe the subject distribution using a contingency table for various time-to-hemostasis measurements with respect to treatments by clopidogrel and clopidogrel+MK-2060, respectively.

Time-to-hemostasis (mins)	Clopidogrel	Clopidogrel + MK-2060
<10		
10-20		
> 20		

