2.2.2 Ongoing Clinical Studies

MK-2060-004:

MK-2060-004 is a double-blind, randomized, placebo-controlled, multiple site, sequential panel, single and multiple dose trial of MK-2060 in adult participants (men and women of non-child bearing potential) with ESRD on HD. As of 14-Dec-2021, 41 participants have been administered at least one IV dose up to 40 mg MK-2060 or placebo. To date, single IV doses up to 40 mg in Part 1 have been generally well tolerated and there have been no treatment related SAEs and no discontinuations due to any drug-related AEs. There have been no AEs suggestive of hypersensitivity. Refer to IB Edition 5 for a detailed overview of Part 1 of the study, and available preliminary PK, PD, and safety results for Part 1.

- Updated Pharmacokinetic Data from MK-2060-004 Part 2 since IB Ed 5:

Analysis of preliminary PK from the single dose portion of MK-2060-004 (Part 1) suggested that a multiple dose regimen (25 mg dose on Day 1, 3, and 5, followed by 3 once-weekly maintenance doses of 25 mg) would result in rapid achievement of the Cmax at steady state. The projected Cmax steady state levels were comparable to what was observed for a single 40 mg IV dose and would provide sufficient PD in ESRD patients.

The IB was revised to include observed multiple dose PK parameters from Part 2 of MK-2060-004. PK parameters from 18 subjects in Part 2 are presented in [Table 2]. The observed PK concentration profiles from the Part 2 multiple-dose participants are consistent with the projected PK concentrations using the Part 1 single dose data, suggesting that the PK of MK-2060 is not time dependent.

Preliminary analysis detected no ADA positive samples over 150 days following a single dose of MK-2060 in Part 1 of MK-2060 PN004 in ESRD participants. Also, in Part 2 following multiple doses of MK-2060, no ADA positive samples were found over 111 days after initiation of dosing.

Table 2 Preliminary Part 2 Plasma Pharmacokinetic Parameters [Geometric Mean (%GCV)] of MK-2060 Following Multiple 60-minute IV infusion Doses of 25 mg QW

C _{max_day1} (nM)	C _{max_day22} (nM)	T _{max_day1} ^a (hr)	T _{max_day22} ^a (hr)	C _{max} Ratio (Day 22 Day 1)	Post-wk1 C _{predose} (nM)				Post-wk1 C _{eoI} (nM)		
					Day 8	Day 15	Day 22	Day 29	Day 8	Day 15	Day 22
32.4 (37.7)	93.4 (31.7)	1.00 (1.00 – 48.00) ^b	1.00 (1.00 – 24.00) ^b	2.68 (33.5)	47.1 (28.1)	44.7 (32.0)	44.8 (36.0)	44.6 (32.1)	91.4 (24.1)	96.8 (32.2)	93.5 (33.3)
^a Median (Min-Max)											

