with MK-2060). Participants will be monitored closely during the infusion with scheduled VS and physical examinations as indicated in the Schedule of Activities. In addition to monitoring for acute reactions to MK-2060, the infusion site will be assessed for signs of reactogenicity, including pain, tenderness, erythema and swelling by study staff, particularly during the first week after infusion. AEs and SAEs will be collected through Day 104.

Time to adequate hemostasis after decannulation of vascular access

A secondary objective of this study is to explore the effect of MK-2060 given as a single and multiple IV dose on time to hemostasis after decannulation of the hemodialysis vascular access site in ESRD patients on clopidogrel therapy. In the dialysis unit after the completion of hemodialysis the dialysis catheters are removed from the dialysis access site (i.e., AV fistula or AV graft). Upon decannulation, pressure is held until adequate hemostasis has been obtained for both the arterial and venous sites. In this study the process is standardized such that change in time to hemostasis from baseline (i.e., average of values obtained from the run-in period) can be assessed (see the operations manual for details).

On three dialysis visits prior to dosing, time to adequate hemostasis for both the arterial and venous sites will be assessed to establish a baseline (mean of three run-in period assessments). Should time to hemostasis be different for arterial and venous sites, the longer of the two should be recorded. This endpoint will then be assessed at the end of the dialysis sessions after each dosing days as specified in the SoA. Change from baseline will be calculated.

Anti-drug antibodies (ADAs) to MK-2060

The presence and titer of ADAs will be measured using validated assays. ADAs can develop to biologics like MK-2060. ADAs may be clinically inconsequential or may change the PK and/or drug efficacy. Moreover, ADAs may lead to safety events, such as acute or delayed hypersensitivity reactions. Thus, the titer of ADAs will be correlated with PK and safety events. If needed, positive ADAs will be further evaluated to determine whether they are able to neutralize MK-2060 activity against FXI. If MK-2060-specific antibodies are confirmed to be present, additional tests will be performed to determine if the antibodies have the ability to neutralize the action of MK-2060.

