4.3.1 Rationale for Dose Interval and Study Design

The ESRD/HD population is the target patient population for MK-2060, and a proportion of ESRD patients are taking antiplatelet therapy, such as clopidogrel. Dosing of MK-2060 with the 1 week loading regimen followed by 1 maintenance dose on Day 8 provides a duration of time where MK-2060 exposures are highest and FXI inhibition/aPTT prolongation is maximized (but not exceeding exposures observed in previous trials in ESRD/HD patients). With the slow clearance of MK-2060, there will be prolonged pharmacology during washout, during which time safety and bleeding-related AEs will continue to be monitored.

Each participant will be dosed and observed until discharge (~24 hours post-dose) for safety/tolerability. 24 hours is sufficient to monitor for initial safety/tolerability and local infusion site reactions and for systemic reactions to infusion. Following discharge, the following measures are being taken in this protocol to ensure the safety of study participants:

- Participants will be informed that they are taking an anticoagulant as a participant in this trial, and that this might increase the risk of bleeding as might occur in surgery, dental procedures, or strenuous exercise/contact sport activities.
- Participants will be excluded if they have planned significant dental procedures, including surgery, or other planned surgical procedures within duration of participation in the trial.
- Participants will be required to avoid scheduling any non-urgent/elective surgical or dental procedures, and to avoid strenuous physical activity and contact sport activities for the duration of the trial.
- Participants will be provided with an identification card and a medical alert bracelet, both of which identify them as participants in an anti-coagulant

research trial and, in the event of an emergency, will serve to notify healthcare providers that they might be at risk for provoked bleeding.

- If local lab aPTT values are > 3-fold above baseline, or local lab PT values are > 1.5 fold above baseline (at any time point), participants will be asked to remain in the clinic for at least 24 hours, and until aPTT/PT values are no longer increasing (upon retest) and at the discretion of the investigator.

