6.1 Study Intervention(s) Administered

The study interventions to be used in this study are outlined in [Table 3](#).

Table 3 Study Interventions

Arm Name	Arm Type	Intervention Name	Intervention Type	Dose Formulation	Unit Dose Strength(s)	Dosage Level(s)	Route of Administration	Regimen/ Treatment Period/ Vaccination Regimen	Use	IMP/ NIMP	Sourcing
MK-2060	Experimental	MK-2060	Drug	Lyophilized Powder	7.5 mg/vial	25 mg	IV Infusion	Week 1: Days 1, 3, 5 Week 2: Day 8	Experimental	IMP	Provided centrally by Sponsor.
EEA =European Economic Area; IMP=investigational medicinal product; IV = intravenous; NIMP=noninvestigational medicinal product. The classification of IMP and NIMP in this table is based on guidance issued by the European Commission and applies to countries in the EEA. Country differences with respect to the definition/classification of IMP/NIMP may exist. In these circumstances, local legislation is followed.											

All supplies indicated in **Table 3** will be provided per the “Sourcing” column depending on local country operational requirements. If local sourcing, every attempt should be made to source these supplies from a single lot/batch number where possible (eg, not applicable in the case where multiple lots or batches may be required due to the length of the study, etc).

Refer to Section 8.1.8 for details regarding administration of the study intervention.

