8.3.4 Assessment of Time to Hemostasis

Assessment of time to adequate hemostasis will be conducted at the conclusion of each onsite hemodialysis session. Procedure for assessment of time to hemostasis will be provided in a separate trial Study Operations Manual by the Sponsor. Baseline time to hemostasis will be established by the assessments performed during the Run-in period.

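### Does section 9.6 need a stated rule for combining repeated post-dose time-to-hemostasis values, or a separate Day 8 criterion?

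*Combined protocol and SAP*

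**What the plan says.** Section 9.6 states that the "posterior probability that the observed mean of time-to-hemostasis of participants is less than 20 will be calculated", using a flat prior, and that success requires a value of at least 0.60. The parameter is the "mean of the time-to-hemostasis measurements for ESRD patients treated with MK-2060".

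The endpoint is repeated. Section 4.2.1.1 says: "This endpoint will then be assessed at the end of the dialysis sessions after each dosing days as specified in the SoA". Section 8.3.4 says: "Assessment of time to adequate hemostasis will be conducted at the conclusion of each onsite hemodialysis session". Section 4.2.1.1 also gives two combining rules: the longer of the arterial and venous times within a session, and the mean of three run-in values as baseline. It gives none for post-dose sessions.

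On scope, section 4.2.1.1 sets the aim to "explore the effect of MK-2060 given as a single and multiple IV dose on time to hemostasis". Section 4.3.1 says the loading week plus the Day 8 dose "provides a duration of time where MK-2060 exposures are highest and FXI inhibition/aPTT prolongation is maximized".

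Section 9.6 also provides mean, SD, median, minimum and maximum for continuous measurements, and extends descriptive summaries to the secondary endpoints where appropriate. Section 9.9 frames the criterion around about 12 subjects.

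**The concern.** Two things look wrong.

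- **Unit of analysis.** A mean of measurements, taken literally, could pool 48 or 60 correlated values as if they were independent. The posterior would then be too narrow.
- **Dilution.** Sessions differ in exposure by design. If MK-2060 prolonged hemostasis in proportion to concentration, sessions at lower exposure would pull the average down. The criterion could be met while the mean at Day 8 exceeded 20 minutes.

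This is the study's only formal hypothesis, and the study is open-label. A loosely defined parameter leaves room to choose the session set after the data are seen.

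**Working it through.** **The plan's own figure.** Section 9.9 gives the simulated chance of success as >X%, with no number, and does not give the mean and SD from MK-2060-004. It cannot be reproduced. With one value per participant and n = 12, P(success) = Φ((20 − μ)/(SD/√12) − 0.2533). This is 0.67 at mean 18 and SD 10, about 1.00 at means of 10-12 with SD 3-8, and 0.40 at a true mean of 20 whatever the SD.

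**Pooling.** With m values per participant and intraclass correlation ICC (assumed), the naive SE is too small by √(1 + (m − 1)·ICC).

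- m = 4, ICC 0.3: √1.9 = 1.38. m = 5, ICC 0.8: √4.2 = 2.05.
- The verdict changes only when the nominal posterior probability lies between 0.60 and Φ(0.2533 × factor), which is 0.64 to 0.70.
- At a true mean of 20, success is 1 − Φ(0.2533/factor). At ICC 0.5 this is 0.436 (m = 4) or 0.442 (m = 5), against 0.40. Over ICC 0.3-0.9 it is 0.43-0.45.

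**Exposure by session.** MK-2060-004 Part 2 used a "25 mg dose on Day 1, 3, and 5, followed by 3 once-weekly maintenance doses of 25 mg". The present schedule is "Week 1: Days 1, 3, 5 Week 2: Day 8", so the two agree through Day 8. Table 2 gives Day 1 Cmax 32.4 nM, Day 8 predose 47.1 nM, Day 8 end of infusion 91.4 nM and Day 15 predose 44.7 nM. Day 3 and Day 5 are not given. Assume mono-exponential decline and superposition, with the end-of-infusion level standing for the session:

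- k = ln(91.4/44.7)/7 = 0.102 per day, so the two-day factor is 0.815.
- Day 3: 32.4 × 0.815 + 32.4 ≈ 59 nM.
- Day 5: 59 × 0.815 + 32.4 ≈ 80 nM going forward, or 47.1 × exp(3k) = 64.0 nM back from Day 8 predose.

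**Share of a Day 8 effect kept** (mean session concentration / 91.4):

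| Sessions | Day 5 = 64 nM | Day 5 = 80 nM |
|---|---|---|
| Four (Days 3, 5, 8, 15) | 0.71 | 0.75 |
| Five (adding Day 1) | 0.64 | 0.67 |

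Wider limits (Day 3 from 32.4 to 91.4, Day 5 from 47.1 to 91.4) give 0.59-0.87 and 0.54-0.77. Their low ends require no accumulation by Day 3 and no decline from Day 5 to Day 8. That fits poorly with a fall from 91.4 to 44.7 over seven days.

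**When the verdict could differ.** Assume a run-in mean of 12 minutes. The Day 8 mean exceeds 20 if the effect is above 20 − 12 = 8. The all-session mean stays below 20 if the effect is under 8/share: 10.6-11.3 with four sessions, 11.9-12.6 with five. The wider limits give 9.2 to 14.7.

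**Chance of success** (assumed SD 8, ICC 0.5, n = 12). The SE is 8/√12 = 2.31 for Day 8, 8√(2.5/48) = 1.83 for four sessions and 8√(3/60) = 1.79 for five.

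- Effect +10: all-session mean 18.4-19.5 minutes. It passes about 50-60% of the time (four sessions) or 67-74% (five), against 13% for Day 8. Under the wider limits it passes 26-81% or 47-88%.
- Effect +4: all-session passes about 99%, Day 8 about 93%.

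**The case for a change.** The strongest case for a change is that the study exists to test the combination with clopidogrel, so reassurance from MK-2060-004 is only indirect. The regimen was chosen to reach high exposure, and in the +10 example the all-session rule passes several times as often as a Day 8 rule. Naming the parameter would cost one sentence and no new data. It would also close off a choice made after seeing open-label results, and tie the SD in section 9.9 to a defined unit.

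Part of this stands. Section 9.6 does leave the session set and the combining step unstated. The damaged Schedule of Activities row shows four post-dose marks, while section 8.3.4 would also bring in Day 1.

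The rest carries less weight. Section 9.6 speaks of the mean of participants, and section 9.9 of about 12 subjects. Both fit one value each, and the run-in average is a ready model for it. Section 4.3.1 describes a period of high exposure, not a single visit, and section 4.2.1.1 covers single and multiple doses, so the all-session mean answers a stated aim. A Day 8 rule gives up precision. By-day summaries are not specified, but nothing in section 9.6 excludes them, so a high Day 8 mean need not be hidden. A mixed model would give nearly the same answers as simple t posteriors when data are complete.

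**Conclusion.** No change to the plan follows. The missing combining rule is a detail that an analyst fills sensibly with one average per participant. Even the naive alternative moves success at the boundary only from 0.40 to about 0.44, because a 0.60 threshold is not sensitive to the width of the posterior.

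Day 8 against all sessions is a fair trade-off, and both readings have support in the text. The true means straddle 20 minutes only for a Day 8 effect above +8 and below about +11 to +13 minutes, close to a doubling of the assumed 12-minute run-in mean. Section 4.2 points the other way: preliminary data suggest no prolongation with MK-2060, and a cited study of clopidogrel in hemodialysis patients found no impact.

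The consequence is limited too. The hypothesis is secondary, section 9.1 calls the study exploratory, and none of the stopping rules in section 6.6.1 uses time to hemostasis.

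The figures rest on assumptions that the documents do not supply: the run-in mean, SD and ICC, an effect proportional to concentration, mono-exponential decline, and superposition for Days 3 and 5.
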